### **3.2.15 Pooling of Centres**

It is not planned to perform a subgroup analysis on individual or groups of centres.

### **3.2.16 Interim/futility analysis**

#### **Phase I**

Safety and radiation exposure data will be reviewed on an ongoing basis during the radioactivity escalation.

#### *Proceeding to the Next Cohort*

The DRB meeting for radioactivity and peptide mass escalation will take place after three subjects of the radioactivity escalation cohort have completed two cycles of Lu-OPS201. The DRB will review all available safety and dosimetry data from the study to decide if the escalation can proceed as planned. If DLTs are reported, a statistical Bayesian modelling approach will be implemented to produce more precise radioactivity-DLT and organ absorbed doses curves to guide the radioactivity selection and predict a radioactivity not exceeding the predicted MTCA/MTSA that could be tested in the next cohort of radioactivity escalation.

If the starting cumulative radioactivity of 9 GBq is not well tolerated, another cohort with a decreased cumulative radioactivity will start. In this case, the cumulative radioactivity could be determined using the statistical Bayesian approach, for example, 7.5 GBq (one administration of 4.5 GBq followed by an administration of 3 GBq, 6 weeks apart (+ up to additional 4 weeks in case of AEs that need to be adequately recovered)).

#### *Stopping Rules for Dose Escalation*

The radioactivity escalation will be stopped as soon as:

- the MTCA and/or MTSA have been defined with good precision; or
- the maximum planned radioactivity of 12.9 GBq, fractionated into two administrations separated by 6 weeks, is administered without safety concerns and is thus defined as the MACA.

SAP Final: Version 2.0: [03 January 2020]

52/57

Once the radioactivity escalation has been completed, the MTCA level may be repeated based on the results of the Bayesian model in a last cohort of three to five subjects with the same peptide mass dose to confirm the safety profile. If the MTCA is not reached and if limiting organ absorbed doses are not exceeded at the highest planned radioactivity (12.9 GBq) and if no individual withdrawal criteria are met, the inclusion of an additional cohort with a higher cumulative radioactivity will be evaluated.

#### *Peptide Mass Dose Evaluation*

In parallel with the radioactivity escalation phase, once the first cycle of a radioactivity level is considered acceptably tolerated by the DRB, the radioactivity level will be repeated with a higher peptide mass dose (700 µg ( $\pm 15\%$ )). Three additional cohorts of three to five subjects will thus be enrolled in the peptide mass dose evaluation.

The DRB for peptide mass dose escalation will meet after the third subject of each cohort has received the first cycle of  $^{177}\text{Lu}$ -OPS201 with DLT assessments performed.

The DRB will review all safety and dosimetry data and allow the peptide mass dose escalation. The cohort with the high peptide mass dose (700 µg) will thus only start when the first cycle of the corresponding radioactivity level tested with 300 µg peptide mass dose has been evaluated by the DRB and has been considered acceptably tolerated.

Moreover, the administration of the second cycle of the peptide mass dose evaluation cohorts can only proceed once the second cycle of the corresponding radioactivity level has been considered acceptably tolerated. The same subject cannot participate in the radioactivity escalation cohort and the peptide mass dose cohort.

At the time of DRB meeting, all cumulative available information will be reviewed.

### **Phase II**

An interim analysis will be performed for futility based on the first stage of Simon's optimal two-stage design within each cohort.

For the SCLC cohort, the first stage consists of 29 subjects. An analysis will be conducted after approximately 29 subjects have been assessed on the ORR. The ORR assessment cut-point for the 29th subject is 6 weeks after Cycle 2 dose. The probability of early termination (PET) after the first stage is 0.6555. If seven responses or less are seen in the first 29 subjects then the trial is stopped. Otherwise accrual continues to a total of 69 response evaluable subjects.

For the BC cohort, the first stage consists of 33 subjects. An analysis will be conducted after approximately 33 subjects have been assessed on the ORR. The ORR assessment cut-point for the 33rd subject is 6 weeks after Cycle 2 dose. The probability of early termination (PET) after the first stage is 0.6374. If four responses or less are seen in the first 33 subjects then the trial is stopped. Otherwise accrual continues to a total of 87 response evaluable subjects.

#### **3.2.17 Role of data review board (DRB)**

The data review board (DRB) for radioactivity escalation, consisting of a team of "permanent" decision makers (the core team), including selected principal investigators and Ipsen personnel, will review the safety and dosimetry data and jointly decide with the sponsor whether to proceed with the enrolment of the next cohort. Details of roles and responsibilities of DRB are described in the DRB charter.

## **4 COMPUTER SYSTEMS, SOFTWARE AND VALIDATION OF PROGRAMS**

### **4.1 Software**

All tables, listings and figures will be produced and statistical analysis performed using SAS® version 9.3 or higher. All outputs will be in Microsoft Word Format.

#### 4.2 Validation programs

Programs will be validated according to CCI

#### 4.3 Restitution of the programs

All programs (including Macros and analysis datasets) producing the tables, listings and statistical output along with associated logs should be given to the sponsor when the tables, listings, figures and statistical analysis has been finalised.

### 5 CHANGES FROM PROTOCOL

Due to Premature Closure of this study, the analysis for the Clinical Study Report was revised. Following data listings outputs are selected.

#### Discontinued subjects

- Subject Disposition (Eligibility Screened Population)
- Inclusion Criteria Description
- Exclusion Criteria Description
- Screening Failures (Eligibility Screened Population)

#### Protocol deviations –

- Protocol Deviations (Eligibility Screened Population)

#### Demographic data

- Demographics (Eligibility Screened Population)
- Tumour Characteristics (Eligibility Screened Population)
- Significant Medical and Surgical History (Eligibility Screened Population)

#### Compliance and/or drug concentration data

- IIP Preparation (Eligibility Screened Population)
- IIP Administration and Extent of Subject Exposure (Eligibility Screened Population)

#### Adverse event listings (each subject)

- All Adverse Events (Eligibility Screened Population)
- Serious Adverse Events (Eligibility Screened Population)
- Adverse Events Leading to Deaths (Eligibility Screened Population)
- Adverse Events with NCI CTC Grade  $\geq 3$  (Eligibility Screened Population)

## 7 APPENDICES

### Appendix 1: Derived Data

The following derived data will be calculated and included in the listings:

#### (1) Age (specified DEMOG table)

Subject age (years) will be derived as (screening date – birth date)/365.25 and truncated to the largest integer that is less than or equal to the calculated result.

#### (2) BMI (specified VSIGN table)

BMI ( $\text{kg}/\text{m}^2$ ) will be derived as  $\text{Weight} \ (\text{kg}) / [\text{Height}(\text{cm})/100]^2$  and rounded to the nearest decimal.

#### (3) Body Surface Area (specified VSIGN table)

Body Surface Area ( $\text{m}^2$ ) will be derived as  $(\text{Weight} \ (\text{kg})^{0.425} \times \text{Height}(\text{cm})^{0.725} \times 71.84) / 10000$  and rounded to the nearest decimal.

#### (4) Changes from baseline

Changes from baseline will be calculated as a difference from baseline (e.g. assessment at the visit – assessment at baseline).

#### (5) Percent change from baseline

Percent reduction from baseline will be calculated as a percentage of decrease from baseline (e.g.  $100 \times (1 - (\text{assessment at the visit}) / (\text{assessment at baseline}))$ ).

If assessment at baseline is zero, percent change will not be calculated. Unless when both assessment at baseline and assessment at the visit are zero, percent change will not be set as zero.

#### (6) Adverse event duration

If the start date of the adverse event is identical to the date of last administration, then " $<1$ " day will be presented, otherwise it will be calculated as (start date - last administration date)+1 and presented in days. If the start date and the associated information do not allow to state about the last dose received (partial start date or start at administration day without knowing if it started before or after the drug intake), all the possible time since last dose will be presented [i.e.: if a subject received a daily administration and reported an AE at second administration day but without indication about before or after the drug intake the time since last dose will be as " $2 / <1$ "]. If the start date is partial, the time since last dose will be presented as an superior inequality (i.e.: for an AE started in FEB2004 after the only administration performed on 31JAN2004, the time since last dose will be as " $\geq 2$ " days). If the start date is missing the time since last dose will not be presented although the AE will be assigned to each dose received before its end date.

#### (7) Concomitant therapy duration

If times are available, the duration of concomitant treatments/physiotherapy etc. will be calculated as (end date/time - start date/time). If at least one time is missing, the duration of concomitant treatments will be calculated as (end date - start date) +1. If the recorded end date is CONT. (for continuing) then the end date will be listed as "ongoing" and the duration will be approximated as " $\geq (\text{last attended visit date} - \text{start date}) + 1$ " day(s). If the start date or the end date are partial, the duration will be presented as an inequality " $\geq xx$ " day(s) [i.e.:  $\geq 2$  where start date=31JAN2004 and end date=FEB2004 or start date=JAN2004 and end date=01FEB2004] but if both are partial or one is missing the duration will not be presented.

**(8) Study day**

Study day will be defined as ‘-1’ for the day prior to treatment and as ‘1’ for the day of treatment (i.e. day 0 does not exist).

**(9) Relative phase**

Relative phase variables describe the event date as pre, during and or post treatment relative to the first study medication intake date. There are two-phase variables:

1. VAR\_SPH describes the start phase of an event relative to the first and the last date of study medication intake
2. VAR\_EPH describes the end phase of an event relative to the first and the last date of study medication intake.

The phase code list consists of

0.5 = indeterminate

1 = pre

2 = during

3 = post

If the event start date is before the start date of study medication or before the start time of study medication, then

VAR\_SPH = 1 (pre).

If the event start date is on or after the start date of study medication and on or before the end date of study medication, then VAR\_SPH = 2 (during)

If the event start date is after the end date of study medication, then VAR\_SPH = 3 (post)

If the event end date is before the start date of study medication, then VAR\_EPH = 1 (pre)

If the event end date is on or after the start date of study medication and on or before the end date of study medication, then VAR\_EPH = 2 (during)

If the event end date is after the end date of study medication, then VAR\_EPH = 3 (post)

As a general rule, relative phase variables should be calculated for all date variables in a panel unless otherwise indicated (e.g.: AE, medical history, prior and concomitant medications, disease related histories, lab data). If dates are incomplete or completely missing, then information on cycle numbers should be used to complete the phases.

Relative phase variables should not be left indeterminate for adverse events, medical history and concomitant medications. It should be completed even in the case where dates are partial or completely missing by using worst-case scenario.

**Worst Case Scenarios for Phase Variables**

Item	Worst case scenario for the start phase _SPH	Worst case scenario for the end phase _EPH
Adverse events	During	During
Medical history	Pre	Pre
Concomitant medication	Pre	During

Phase variable should be left as Indeterminate.(0.5), only when no reasonable assumptions can be made due to missing or incomplete dates.

#### (10) Relative days

Relative days based on the very first study medication infusion/intake date (D1, Cycle 1) and the very last study medication infusion/intake date (D1, Cycle n) or first day of a given Cycle.

Four types of relative days (VAR\_SrS, VAR\_SrE, VAR\_ErS and VAR\_ErE) will be calculated for any event defined with start and stop dates (e.g.: AE, Prior and Concomitant medication, Medical history etc.) and three types of relative days (VAR\_ArS, VAR\_ArE and VAR\_ArCx1) will be calculated for assessments (e.g.: lab parameters, ECG, vitals etc.) unless otherwise specified.

For example: if VAR=AE then

##### **AE\_SrS: Relative days from start of the event to start of study drug administration.**

AE\_SrS will be calculated by using either of the following two formula:

- If AE onset was on or after initiation of study medication then  
$$AE_{SrS} = \text{event start date} - \text{first study drug administration date} + 1$$
- If AE onset was before initiation of study medication then  
$$AE_{SrS} = \text{event start date} - \text{first study drug administration date}$$

##### **AE\_ErS: Relative days from end of the event to start of study drug administration**

AE\_ErS will be calculated by using either of the following two formula:

- If AE end date was on or after initiation of study medication then  $AE_{ErS} = \text{event end date} - \text{first study drug administration date} + 1$
- If AE end date was before initiation of study medication then  $AE_{ErS} = \text{event end date} - \text{first study drug administration date}$

**Relative assessment days based on the first drug administration will be calculated as following:**

- If LAB sample date was on or after first drug administration then
- $LAB_{ArS} = LAB \text{ sample date} - \text{first date of study drug administration} + 1$
- If LAB sample date was before first drug administration then
- $LAB_{ArS} = LAB \text{ sample date} - \text{first date of study drug administration}$

**Relative assessment days based on the last drug administration will be calculated in a similar fashion.**

- If LAB sample date was on or after last drug administration then  
$$LAB_{ArE} = LAB \text{ sample date} - \text{last date of study drug administration} + 1$$
- If LAB sample date was before last drug administration then  
$$LAB_{ArE} = LAB \text{ sample date} - \text{last date of study drug administration}$$

**Relative assessment cycle days based on the Day 1 of cycle X will be calculated in the similar fashion.**

- $LAB_{ArCx1}$ : Relative assessment cycle days from lab sample date to D1 of cycle X (Cx1) will be calculated by using formula
- $LAB_{ArCx1} = \text{lab sample date} - Cx1 + 1$

(Note : the relative assessment cycle days based on the day one of cycle one (C1D1) is the equal to relative assessment days based on first drug administration (i.e.: VAR\_ArS).

#### (11) AE duration

AE duration will be set equal to the value recorded on the CRF if the duration is less than 24 hours. If the duration is not specified, then it will be calculated by using “AE\_ErS - AE\_SrS” recorded in days. If the end date is missing because the adverse event was ongoing then the duration will be listed as “ongoing”.

(12) A **nadir** for a subject is defined as the lowest laboratory value or tumor evaluation (volume or longest diameter) during the whole treatment period (all cycles combined) among all infusions for that subject and a nadir for a cycle is defined as the lowest laboratory value or tumor evaluation (volume or longest diameter) in that cycle. The day to nadir in a cycle is the number of days between the nadir and the first date of study medication intake of that cycle.

(13) The **time to recovery** will be calculated for WBC, neutrophils, haemoglobin and platelets with toxicities grade 3 or 4. Recovery is defined as the return to grade 0, 1 or baseline level. The time to recovery is the number of days between the nadir and the date of first assessment of the recovery.

For the calculation of the nadir, day to nadir and time to recovery of haematological events, the cycles where G-CSF or red blood cell packs or platelets units have been given will be censored for the related parameter as following: WBC and neutrophils will be censored when G-CSF or total blood products are given, haemoglobin will be censored when red blood cell packs or total blood products or erythropoietin products are given and platelets when platelets units or total blood products are given. If the haematological supporting drugs were started before the nadir then any following assessment of this nadir such as day to nadir and time to recovery will be censored. If this therapy was initiated after the nadir is reached, only time to recovery will be censored. A listing detailing the censoring will be provided.

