### 1.3.2.2 Safety assessments

The primary safety variable is the occurrence of Dose-Limiting Toxicities (DLTs) during Cycle 1 or Cycle 2.

The DLTs are defined for any of the following Investigational Radio-Pharmaceutical Product-related (IRPP-related) AEs according to National Cancer Institute Common Terminology Criteria Adverse Event (NCI-CTCAE) scale version 5.0 that occur during the defined DLT assessment period (from the first administration of Lu-OPS201 to 6 weeks after the second administration):

- Grade 4 neutropenia lasting for seven or more consecutive days.
- Grade 3 and 4 febrile neutropenia.
- Grade 4 thrombocytopenia for seven or more consecutive days.
- Grade 3 thrombocytopenia complicated by a bleeding event.
- Grade 4 anaemia.

- Grade 3 anaemia requiring transfusion.
- Grade 3 or higher laboratory abnormalities of aspartate amino transferase/alanine amino transferase (AST/ALT) and/or bilirubin, with the following exceptions:
  - for subjects with Grade 1 AST/ALT at baseline (>upper limit of normal (ULN) to 3xULN), a AST/ALT level of >7.5xULN will be considered a DLT.
  - for subjects with Grade 2 AST/ALT at baseline (>3xULN to 5xULN), a AST/ALT level > 10xULN will be considered a DLT.
- any Grade 3 or higher acute kidney injury (creatinine >3x baseline or >4.0 mg/dL).
- Grade 3 or higher non-haematological toxicity excluding:
  - Grade 3 nausea, vomiting or diarrhoea for less than 72 hours with adequate supportive care
  - Grade 3 fatigue lasting less than a week
  - Grade 3 or higher electrolyte abnormality that lasts for less than 72 hours, is not clinically complicated and resolves spontaneously or with conventional medical interventions
  - Grade 3 or higher amylase or lipase not associated with symptoms or clinical manifestations of pancreatitis
- any toxicity related to Lu-OPS201 resulting in a treatment delay of more than 4 weeks due to delayed recovery to baseline or resolution of any AE of Grade 2 or more (exception of alopecia and lymphopenia).
- Grade 5 toxicity (death)

**DLT Assessment:** During the DLT assessment period (from first administration of Lu-OPS201 to 6 weeks after the second administration), two assessments over 6 weeks each will be performed. The first, between first and second administration and the second, between second administration and EOCT visit.

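### The fallback rule for AE duration in SAP Appendix 1 item (11) lists events of equal length as 6 or 7 days depending on whether they span first dose, and item (6) carries the wrong title

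*SAP*

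**What the plan says.** Appendix 1 item (11) of the SAP, on AE duration, works in steps. First, "AE duration will be set equal to the value recorded on the CRF if the duration is less than 24 hours". Next, "If the duration is not specified, then it will be calculated by using" AE_ErS − AE_SrS, in days. An event that has not ended is listed as ongoing.

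The two terms are defined in item (10). For the start day, "If AE onset was on or after initiation of study medication then" it is the event start date minus the first administration date, plus 1; "If AE onset was before initiation of study medication then" it is the same difference without the 1. The end day, AE_ErS, follows the same two branches, applied to the end date. Item (8) confirms that the day before treatment is −1, the day of treatment is 1, and there is no 0.

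Item (7) sets the parallel rule for concomitant therapy. With times, it subtracts start from end. If a time is missing, "the duration of concomitant treatments will be calculated as (end date - start date) +1".

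Item (6) is also titled as adverse event duration. It begins "If the start date of the adverse event is identical to the date of last administration" and goes on to compute AE start date minus last administration date, plus 1. Its own text calls the result time since last dose.

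The opening line of Appendix 1 says that the derived data go into the listings. Section 5, written after premature closure, keeps listings of all AEs, serious AEs, AEs leading to death and AEs of Grade 3 or higher.

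**The concern.** A difference between two numbers on a scale with no zero is not a count of days once the zero point is crossed. Item (11) takes such a difference and so does not apply one counting rule to all events. An event's listed length depends on where it falls relative to first dose as well as on how long it lasted.

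There are two further problems in the same appendix. AE durations and date-only concomitant therapy durations are counted differently. And two items claim the name AE duration, one of which computes something else.

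What is at stake is the accuracy and consistency of the durations in the AE listings that Section 5 retains.

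**Working it through.** **The SAP's own example.** Item (7) gives a therapy starting 31JAN2004 and ending at an unspecified date in FEB2004, and states at least 2 days. At the earliest possible end date, 1 February − 31 January + 1 = 2, as stated. Without the added 1 it would be 1. So the date-only rule in item (7) counts both end dates.

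**Item (11) in general.** Let f be the first administration date, s the event start date and e the event end date. Inputs are the item (10) formulas for AE_SrS and AE_ErS.

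- Start and end on or after f: (e − f + 1) − (s − f + 1) = e − s.
- Start and end before f: (e − f) − (s − f) = e − s.
- Start before f, end on or after f: (e − f + 1) − (s − f) = e − s + 1.

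**With numbers.**

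| Event (study days) | Calendar dates covered | AE_SrS | AE_ErS | Item (11) | e − s + 1 | Item (11) plus 1 |
|---|---|---|---|---|---|---|
| Day 1 to 7 | 7 | 1 | 7 | 6 | 7 | 7 |
| Day 10 to 16 | 7 | 10 | 16 | 6 | 7 | 7 |
| Day −10 to −4 | 7 | −10 | −4 | 6 | 7 | 7 |
| Day −1 to 6 | 7 | −1 | 6 | 7 | 7 | 8 |
| Day −3 to 4 | 7 | −3 | 4 | 7 | 7 | 8 |
| Day 10 only | 1 | 10 | 10 | 0 | 1 | 1 |
| Day 10 to 17 | 8 | 10 | 17 | 7 | 8 | 8 |

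Five events of seven dates are listed as 6 or 7 days. An on-treatment event of eight dates and a seven-date event spanning first dose are both listed as 7. The calendar-date formula is right in every row. Adding 1 to item (11) moves the error to the spanning events.

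**A related slip.** LAB_ArCx1 in item (10) is the sample date minus Day 1 of the cycle, plus 1, with no branch for earlier samples. A sample taken the day before gives −1 + 1 = 0. Item (8) says there is no Day 0. LAB_ArS gives −1 for the same sample in Cycle 1, yet the note under LAB_ArCx1 says the two are equal there.

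**The case against.** The strongest defence is that end minus start is a legitimate measure of elapsed days. An event recorded on seven calendar dates can last anything from just over five to seven elapsed days. The SAP also has no single inclusive convention: item (7) omits the 1 when times are available, and item (13) counts days between two dates. This stands as far as it goes. Listing 6 for seven dates is not, taken alone, an error. But it does not rescue item (11), because no one convention yields both 6 and 7 for the same number of dates.

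The reach is also limited. The formula applies only where no duration is specified and the event has ended, and a CRF value is used for events under 24 hours. The 0-day result needs a same-day event with no CRF duration. This stands too.

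A reader might infer that the rule hides dose-limiting toxicities. Section 1.3.2.2 has cut-offs at this length, such as "Grade 4 neutropenia lasting for seven or more consecutive days" and the exclusion of "Grade 3 fatigue lasting less than a week", and in a cohort of three one missed case would be 1/3, or 33 percentage points. The document does not support that. Nothing feeds item (11) into DLT classification. The haematological criteria count consecutive days at Grade 4, which need not equal the span of the AE record. The data review board reviews the safety data, including DLTs. Section 5 keeps no DLT output. The inference would need an event of exactly seven dates, no recorded duration, and a DLT call made from item (11), and the last of these is an assumption.

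For item (6), only the title is wrong, since the body makes its purpose clear. For LAB_ArCx1, the text says the calculation is similar to the branched ones before it, so the intent is recoverable.

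**Conclusion.** The concern holds as a derivation error in the AE listings. Item (11) gives end minus start for events wholly on one side of first dose and end minus start plus 1 for events that span it. The size is one day per affected event: 6 against 7 for seven dates. It also differs by one day from the date-only rule in item (7). Item (6) is mis-titled.

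This rests on reading items (8), (10) and (11) literally, and it applies only to ended events without a specified duration. A consequence for the seven-day DLT criteria would follow only if the item (11) duration were used to check them, which the SAP does not state. The point is a minor correction, still worth making because the AE listings survive the reduced reporting.

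**What to change.** - Item (11): where no CRF duration is given and the AE has ended, derive duration as (AE end date − AE start date) + 1 from calendar dates. Do not add 1 to AE_ErS − AE_SrS. The calendar form also needs no first-dose date, which helps because the retained listings cover everyone who signed consent.
- Item (6): retitle it *Time from last administration to AE onset*.
- LAB_ArCx1, as a minor alignment: write in the branch for samples before Day 1 of the cycle, without the added 1, so that it agrees with item (8), with LAB_ArS and with its own note.

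The cost is three derivation lines, with no change to data collection or design.
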